5.12 Co-Interventions

We propose a pragmatic design whereby all co-interventions will be left to the discretion of the treating physician, who will be blinded to treatment assignment. However, we will carefully record use of relevant co-interventions. Unblinded administration of intravenous corticosteroids will constitute a protocol violation, except for patients with COVID-19.

Patients with COVID-19 will receive dexamethasone once daily at a dose of 6 mg for 10 days, as their standard of care

5.12.1 Unauthorized treatments

- Hydrocortisone and other corticosteroids whatever the dose and the route (except local administration, nebulization not being considered as a local administration) are not allowed, except dexamethasone 6mg per day for 10 days in patients with COVID-19. If an unavoidable indication appears during patient stay (e.g. autoimmune disease) the patient should be treated. In this case, the study treatment will be stopped to avoid unnecessarily high-dose of hydrocortisone. However, short-duration administration of open corticosteroids will be allowed for prevention of post-extubation laryngeal edema.

- Continuous infusion of neuromuscular blocking agents is to be avoided. In the case it will be indicated (e.g. for severe ARDS), this will be for the shorter period possible and an interruption of the infusion will be planned every 12 hours, to insure not to prolong the treatment longer than necessary.

5.12.2 Authorized treatments

All other treatments are allowed according to best practice guidelines whenever available (Rhodes 2017). These treatments ay include for example, mechanical ventilation, renal replacement, vasopressor therapy, thiamine, nutrition therapies including multivitamins, intravenous fluids, blood products, sedatives, and antimicrobials. We will carefully record the use of these treatments to detect and report any imbalances between the treatment groups.

Patients with COVID-19 will receive open-label dexamethasone at a dose of 6 mg once daily for 10 days (RECOVERY 2020; Sterne 2020).

5.13 Methods for monitoring compliance with the treatment

Study drugs will be administered to patients in the intensive care unit setting for 7 days and recorded with the registered monitoring form of administration. This form will be used to track the administration of study treatments and will be kept in the patient chart. This track log will be monitored by the study CRA.

5.14 Management of Potential Risks to Participants

The safety profile for hydrocortisone and fludrocortisone is remarkably favourable (Annane 2018; Venkatesh 2019). A potential risk is the acquisition of neuromuscular weakness which may more likely seen when corticosteroids are combined with neuromuscular blocking drugs. We will limit the use of curares during the study according to best practice guideliens (Rhodes 2017), and neuromuscular function/strength will be monitor and will be recorded as an outcome in this trial.

Another potential risk, is corticosteroids induced diabetes mellitus. This complication is usally seen with much higher dose and more prolonged exposure to corticosteroids than it will be in this trial. Nontheless, according current best practice guidelines for the management of sepsis (Rhodes et al SSC), blood glucose levels will be kept below 180mg/dl by intravenous insulin therapy whenever needed.

Patients treated in ICU are already monitored very closely. Any serious adverse event (SAE) will be managed immediately by the treating team. Unexpected events will be reported to the research team within 24 hours (see 6.6).

5.14 Outcome Measures

5.14.1 Primary Outcome

The primary outcome will be 90-Day organ dysfunction, ventilation and vasopressors free survival after randomization, which is a composite of day 90 mortality and survival free days off vasopressors and mechanical ventilation, and with SOFA score >6 (Laterre 2019). Such composite outcomes are increasingly used in ICU trials as reliable patient-centered outcomes (Kalkman 2015; Mehta 2017; Semler 2018).

Data on the vital status at day 90 after randomisation will be collected from the medical files (including electronic medical files for the entire hospital) and phone calls to patients and their designated contact persons. The primary endpoint is a binary variable. Patients will be classed as positive outcome if they are alive at day 90 and free of vasopressor therapy, mechanical ventilation and organ dysfunction. Patients

will be classed as negative outcome if they either died in the first 90 days after randomisation or if they remained vasopressor or mechanical ventilation dependent or with a SOFA score >6 beyond 28-days.

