Main objective and primary endpoint	To compare the effect hydrocortisone plus fludrocortisone vs. placebo on a composite of death or persistent organ dysfunction – defined as continued dependency on mechanical ventilation, new renal replacement therapy, or vasopressors – assessed at 90 days on intensive care unit (ICU) adults and having different biological profiles for immune responses and corticosteroids bioactivity The primary endpoint is death or persistent organ dysfunction (defined as continued dependency on mechanical ventilation, renal replacement therapy, or vasopressors) and with SOFA score >6 up to 90 days.						
Secondary objectives	 Mortality and health-related quality of life at 6 months; 						
and endpoints	 Daily organ function (SOFA score days 1, 2, 3, 4, 7, 10, 14, 28, and 90); 						
	 Daily secondary infections (up to 90 days) Daily blood and urinary levels of glucose, sodium and potassium (up to 28 day) Daily gastroduodenal bleeding (up to 28 day) Daily cognitive function and muscles' strength (days 1 to 28, 90 and 180 days) 						
Study design	Multi-arms Parallel blinded randomized controlled trial preceded						
	by a 6-month run-in observational period. Observational phase (run-in period) Interventional phase. 						
Inclusion Criteria	1. Patients ≥18 years old;						
observational phase: (N°1,2,3,4,6,7,8,9) interventional phase:	 Admitted to ICU with proven or suspected infection as the main diagnosis; Community acquired pneumonia related sepsis OR vasopressors dependency (norepinephrine, epinephrine, vasopressin, dopamine, phenylephrine) OR septic shock (Singer 2016: vasopressor to maintain mean blood pressure of at least 65 mmHg and lactate levels above 2 mmol/l) OR acute 						
(N°1,2,3,4,5,6,7,8).	 respiratory distress syndrome (ARDS – Ranieri 2012: a- acute onset, i.e. within one week of an apparent clinical insult and with progression of respiratory syndrome, b- bilateral opacities on chest imaging not explained by other pulmonary pathologies, e.g. pleural effusion, atelectasis, nodules etc, c-no evidence for heart failure or volume overload, d- PaO2/FiO2 ≤ 300 mm Hg, - PEEP ≥ 5 cm H2O Patient who has signed an informed and written consent whevener he/she is able of consent, if not, if not ascent from his/her representant whenever he/she is present at time of screening for inclusion 						

	5. Patients who have been tested for one or more RECORDS
	specific biomarkers:
	a. CIRCI
	b. Endocan
	c. GILZ
	d. CPD

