2.1 PRIMARY OBJECTIVES OF EACH ANALYSIS BY BIOLOGICAL MARKER

To compare the effect hydrocortisone plus fludrocortisone vs. placebo on a composite of death or persistent organ dysfunction – defined as continued dependency on mechanical ventilation, new renal replacement therapy, or vasopressors – assessed at 90 days on intensive care unit (ICU) adults and having different biological profiles for immune responses and corticosteroids bioactivity.

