2.2 SECONDARY OBJECTIVES OF EACH ANALYSIS BY BIOLOGICAL MARKER

- To compare the effect of hydrocortisone plus fludrocortisone vs. placebo on:
 - 1) 6-month mortality;
 - 2) 6-month HRQoL;
 - 3) organ function (days 1, 2, 3, 4, 7, 10, 14, and 28 if in ICU);
 - 4) hyperglyceamia as defined by glucose levels of >8.3 mmol/L (150mg/dL) (daily up to day 28)
 - 5) hypernatremia as defined by serum sodium levels of >150mmol/L (daily up to day 28)
 - 6) secondary infection (daily up to day 90)
 - 7) beeding in the gastrointestinal tract defined by clinical evidence of active bleeding and need for blood transfusion OR hemostatic endoscopic or surgical procedures
 - 8) neurological cognitive dysfunction defined as by low score on the PROMIS Adult cognitive function score (appendix 15.4.7)
 - 9) neuromuscular weakness defined as a grade of 2 or more on Muscular Disability Rating Scale (MDRS) (appendix 15.4.6)

[figure not shown]

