5.8 Table or diagram summarising the chronology of the study

							Da	ays						6 months
	0	1	2	3	4	5- 6	7	8- 9	10	11- 13	14	28	90	
Verification of inclusion and exclusion criteria	X													
Informed consent	Х													
Source of infection		х												
Severity of illness (SAPS II score)		x												
Sepsis data		х												
Pre-existing comorbidities (Charlson comorbidity index, Clinical Frailty Score)		x												
Randomization* (Interventional phase)		х												
Dispensation of treatments		X	X	Х	X	Х	Х							
Biological samples<	Х	Х	x	х	х	х	х	х	x	х	х	x		
Additional Biological samples (biomarqueurs)	X	Xa					X							
Protocol adherence ^b		х	Х	Х	Х	Х	Х							
Co-interventions ^c		Х	Х	х	х	Х	х	Х	х	х	Х	Х	х	
Death or persistent organ dysfunction ^d		х	x	x	х	х	x	х	х	х	x	х	х	x
Vasopressor dependency		х	x	x	х	х	x	х	х	х	x	Х	х	
Organ function including renal function (SOFA score)*	Х	x	x	X	X		X		x		X	x		
HRQoL (EQ-5D-5L) ^e , Promis		x										х	х	x
Serious adverse events*		x	Х	Х	Х	х	x	х	х	х	х	х	x	X

^aMust be collected before the first dose of investigational product. Samples include blood, urine, cells, exhaled air

^bReceipt of every planned dose according to schedule until completion of 7-day treatment protocol, samples collected per protocol instructions, biomarkers collected before the first dose of investigational product.

^cAdministration of mechanical ventilation, renal replacement, vasopressors, vitamin C, thiamine, intravenous fluids, blood products, sedatives, and antimicrobials. Daily data until ICU discharge or 28 days (whichever comes first).

^dDependency on mechanical ventilation, renal replacement, or vasopressors. eEQ5D to be filled at 3 and 6 months

* Interventional trial

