9 STATISTICAL ANALYSIS

9.1 SAMPLE SIZE DETERMINATION

We will enroll a total of at most 1800 patients. Sites are expected to enroll at least 1 or 2 patients per month.

Adaptive outcomes

The goal is to develop an adaptive clinical trial design which evaluates the therapeutic intervention of targeted therapy, identifies subset of subjects who respond better to the experimental therapy.

Sequential analyses will use the number of vasopressor-free days at day 28 as the measure of efficacy, and the occurrence of severe adverse events within the first 28 days as the measure of toxicity. According to the literature (the APPROCCHS trial), the number of vasopressor-free days at day 28 in the hydrocortisone+fludrocortisone group was 17.1 ± 10.8 versus 15.0 ± 11.1 in the placebo group. Thus, a sample of 176x2=352 patients achieves 80.04 % power to reject the null hypothesis of equal means when the mean difference between arms is 3 days with SD of 10 days, and with a significant level (alpha) of 0.05 using a two-sample t-test. For interactions to be detected with the same power as the overall effect, sample sizes should be inflated (Brookes 2004); estimated here at a multiple of fourfold; therefore, to handle potential dropouts, a sample of 1800 patients was considered to be enrolled.

Note that Bayesian inference will be used for sequential analyses, so that no inflation of type I error rate is to be corrected.

Primary outcome

To detect a 10% absolute risk reduction (from 45% to 35%) in the day 90 mortality, a sample size of 373 evaluable patients per arm (thus a total of 746 patients) is required to reach a 80% power. The planned sample of 1800 patients will achieve a 99.16%

power to reject the null hypothesis of equal mortality when the difference between arms is 10% overall, and with a 5% alpha level.

Sample sizes were computed using PASS 15 software (2017).

The power to detect this difference within each group of analysis will depend on the prevalence of each biomarker of interest.

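### The primary outcome is defined in incompatible ways across the protocol, and the power statement in section 9.1 is tied to day-90 mortality instead of the composite

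*Protocol*

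**What the plan says.** Section 2.1 gives the primary objective as a comparison on death or persistent organ dysfunction, the latter "defined as continued dependency on mechanical ventilation, new renal replacement therapy, or vasopressors", assessed at 90 days. The objective in the Study Summary and the restatement in section 7.3.2.3 agree with it.

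The endpoint sentence in the same Study Summary row is different. Persistent organ dysfunction is there "defined as continued dependency on mechanical ventilation, renal replacement therapy, or vasopressors) and with SOFA score >6 up to 90 days". RRT is no longer limited to new RRT, and a SOFA condition has appeared.

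Footnote d to the schedule in section 5.8 names ventilation, RRT (not limited to new) and vasopressors, without SOFA.

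Section 5.14.1 states that the endpoint is binary and gives two rules. Success: "Patients will be classed as positive outcome if they are alive at day 90 and free of vasopressor therapy, mechanical ventilation and organ dysfunction". Failure: death in the first 90 days, or "if they remained vasopressor or mechanical ventilation dependent or with a SOFA score >6 beyond 28-days". Neither rule names RRT.

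Under its *Primary outcome* subheading, section 9.1 begins: "To detect a 10% absolute risk reduction (from 45% to 35%) in the day 90 mortality". It derives 373 evaluable patients per arm for 80% power, and 99.16% power with 1800 patients, against a null hypothesis of equal mortality.

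**The concern.** These are differences of substance. They concern which organ supports count, whether SOFA >6 counts and how it combines with the supports, and when status is judged. Each can move a patient from success to failure. Section 5.14.1, where the endpoint is made operational, also conflicts with itself in consecutive sentences.

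If the choice is made after data have accrued, the headline result is open to selection among definitions. Section 2 applies the primary objective to each analysis by biological marker, so the ambiguity recurs in every cohort.

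The stated power does not describe the stated primary outcome. Day-90 mortality is not listed as a secondary outcome either: section 5.14.2 lists mortality at days 7, 14 and 28 and at 6 months.

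**Working it through.** **1. The definitions side by side**

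| Place | Organ support counted | SOFA >6 | Time |
|---|---|---|---|
| Study Summary (objective), 2.1, 7.3.2.3 | ventilation, new RRT, vasopressors | not used | day 90 |
| Study Summary (endpoint) | ventilation, any RRT, vasopressors | joined by *and* | up to day 90 |
| 5.8, footnote d | ventilation, RRT, vasopressors | not used | row marked through day 90 and 6 months |
| 5.14.1, success rule | ventilation, vasopressors | via organ dysfunction, which 5.14.2 defines as SOFA >6 | day 90 |
| 5.14.1, failure rule | ventilation, vasopressors | joined by *or* | beyond day 28 |
| 9.1, primary outcome | none (mortality only) | not used | day 90 |

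**2. Three test patients, all alive at day 90**

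- *A: ventilated continuously to day 50, then weaned; free of support with SOFA 6 or less at day 90.* The success rule of 5.14.1 gives success. The failure rule gives failure, because the patient was still dependent after day 28. Reading the failure rule as requiring unbroken dependency does not help, since this patient's dependency was unbroken.
- *B: on new RRT at day 90; off ventilator and vasopressors, with SOFA 6 or less, throughout days 28 to 90.* Failure under 2.1, success under 5.14.1.
- *C: still ventilated at day 90, SOFA 6 or less.* Failure under 2.1 and 5.14.1. Not a failure under the Study Summary endpoint, if its *and* is read as a joint condition.

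**3. Is SOFA measured at day 90?** The Study Summary lists a day-90 SOFA among the secondary endpoints. Section 2.2 lists "organ function (days 1, 2, 3, 4, 7, 10, 14, and 28 if in ICU" and stops there, and the SOFA row in 5.8 also ends at day 28. The day-90 data list in 5.5 contains neither SOFA nor laboratory values. The documents conflict, and a day-90 SOFA is not assured for patients already discharged.

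**4. The plan's own power figures.** Inputs from 9.1: 45% versus 35%, 5% alpha (two-sided assumed), 80% power; 1:1 allocation from the Study Summary.

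- Unpooled variance: n = (1.960 + 0.842)² × (0.45×0.55 + 0.35×0.65) / 0.10² = 372.8, so 373 per arm, as in 9.1.
- Pooled variance under the null: n = [1.960×√(2×0.40×0.60) + 0.842×√0.475]² / 0.10², which rounds up to 376 per arm, as in the Study Summary.
- Power at 900 per arm, unpooled: Φ(0.10/√(0.475/900) − 1.960) = 0.9916, the stated 99.16%.

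The figures are right for those rates, and 373 versus 376 is only the choice of variance.

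**5. The same calculation on the composite.** The protocol gives no composite rate. Every version counts death, so the control composite rate cannot be below control mortality. Control rates of 45% to 60% and the three differences below are therefore assumptions. The 6.5 points is the crude mortality reduction quoted in section 1.4.2, applied here to the composite. The table uses pooled variance and shows patients per arm for 80% power, with power at 900 per arm in brackets.

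| Control rate | 10 points | 6.5 points | 5 points |
|---|---|---|---|
| 45% | 376 (99.1%) | 903 (80%) | 1534 (57%) |
| 50% | 388 (99.0%) | 924 (79%) | 1565 (57%) |
| 55% | 392 (98.9%) | 927 (79%) | 1565 (57%) |
| 60% | 388 (99.0%) | 911 (80%) | 1534 (57%) |

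With unpooled variance, the 10-point case needs 385 per arm at 50% versus 40% and 389 at 55% versus 45%.

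**The case against.** The strongest reply is that much of this is loose drafting. Section 5.14.1 says plainly that the endpoint is binary, so its opening mention of free days can be set aside. The Study Summary's *and* is ungrammatical, and 5.14.1 uses *or*, so patient C rests on one possible reading. The Study Summary gives 45% to 35% without naming an endpoint, so mortality in 9.1 may be a slip of the pen. All of that is fair. It does not remove patient A, who is classed both ways within one paragraph, or patient B, who turns on whether RRT counts at all.

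A reader might infer more than the documents support:

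- *That the SOFA component cannot be scored at day 90.* The Study Summary does list it, section 5.4 collects daily data to day 90 for patients still in the ICU, and section 5.15 provides for imputing missing SOFA by rules in the statistical analysis plan. What stands is the conflict in the schedule.
- *That organ support is not recorded at day 90*, from footnote c in 5.8 ("Daily data until ICU discharge or 28 days (whichever comes first"). Its own table row is marked at day 90, and sections 5.4, 5.5 and 5.15 collect support to day 90.
- *That the sample size is wrong.* With a 10-point difference on the composite it barely changes.
- *That switching definition would move the treatment effect by a known amount.* The protocol gives no figure for how many patients recover between days 28 and 90. A shift in the event rate shared by both arms is also not a shift in the difference between them.

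**Conclusion.** The contradiction is real and needs correcting. The protocol holds several incompatible primary outcomes, differing on RRT, on SOFA >6 and on timing, and the two classification rules of 5.14.1 are not complements. Patients A and B establish this without any assumption about event rates; patient C adds to it only on the joint reading of the Study Summary.

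The power statement is arithmetically sound but attached to the wrong endpoint. Its consequence depends on an effect size that the protocol does not state. Power for the overall comparison with 1800 patients is about 99% if a 10-point difference holds on the composite, about 80% at 6.5 points and about 57% at 5 points. This is a missing assumption, not a demonstrated shortfall. How many patients change class between definitions, and in which arm, cannot be determined from the protocol.

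**What to change.** Before any unblinded analysis, align the Study Summary, 2.1, footnote d of 5.8, 5.14.1, 7.3.2.3 and 9.1 on one binary definition that states:

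- one component list, with RRT in or out and, if in, new or any;
- one assessment time or window;
- one rule for whether SOFA >6 counts and whether it joins by *and* or *or*;
- success as everything that is not failure.

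Nothing in the protocol shows which version should prevail, so that choice is the sponsor's. If SOFA stays in the primary outcome, 2.2, 5.5 and 5.8 should schedule it at day 90, including for discharged patients. If not, it should be removed from the primary endpoint in the Study Summary and 5.14.1.

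Restate 9.1 on the composite with an explicit control rate and difference, and list day-90 mortality as a secondary outcome.

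The cost is a protocol amendment. If it is a substantial modification, section 11.4.5 requires ethics committee approval and regulatory authorisation. No extra patients are needed to make the definitions agree, and no extra assessments unless SOFA is kept.

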5.14.2 Secondary Outcomes

The secondary outcomes will include:

1) Mortality at 7, 14, 28 day and 6 months.

2) Vasopressor free days: defined as the number of days with permanent hemodynamic stability in the absence of any vasopressor agent, norepinephrine, phenylephrine, epinephrine, dopamine, vasopressine or its analogs, and soever. When a patient will die on vasopressor therapy, the corresponding vasopressor free day will be 0.

3) Mechanical ventilation free days: defined as the number of days with permanent appropriate oxygenation while the patients is extubated and breathing spontaneously, i.e. no need for non invasive ventilation, high flow oxygen or CPAP. Other uses of non-invasive ventilation (e.g., chronic night-time use for chronic obstructive pulmonary disease) are not counted. When a patient will die on mechanical ventilation or will be discharge home on mechanical ventilation, the corresponding mechanical ventilation free day will be 0.

4) Organ dysfunction free days: Organ function (including renal function) will be assessed by the SOFA score (Vincent 1996). Organ dysfunction will be defined by a SOFA score of > 6 (Annane 2018). Organ dysfunction free days are defined by the number of days with os total SOFA score of 6 or less. When a patient will die on vasopressor therapy, the corresponding vasopressor free day will be 0.

5) HRQoL in 6-month survivors assessed by the EuroQol-5D (EQ-5D). This questionnaire is a standardised measure of health status developed to provide a simple, generic measure of health for clinical and economic appraisal. It is made up for two components; health state description and evaluation. The health status is measured in terms of five dimensions; mobility, self-care, usual activities, pain/discomfort, and anxiety/depression. In evaluation part, the respondents evaluate their overall health status using the visual analogue scale. See Figure 4.

6) Proportion of patients with a decision to withhold and/or withdraw active treatments

7) ICU and hospital length of stay

8) Rate of re-admission to the ICU during the 180 days after randomization

9) Safety endpoints:

- Proportion of patients affected by any serious adverse events associated with corticosteroids, among the following: hospital-acquired infections, hyperglycemia, hypernatremia, neurological disorders (coma, stroke or muscle weakness, as defined below) during the 90 days after randomization
- Coma will be defined as a Glasgow coma score < 8

- Neurologic sequelae will be assessed according to the score on the Muscular Disability Rating Scale (MDRS), with a score of 1 indicating no deficit, 2 minor deficit with no functional disability, 3 distal motor deficit, 4 mild-to-moderate proximal motor deficit, and 5 severe proximal motor deficit.
- Proportion of patients affected by hospital-acquired infections (CTINILS. Définition des infections associées aux soins. 2007)
- Number of episodes of hyperglycemia (blood glucose levels >150mg/dl) during ICU stay (or up to day 90, whichever occurs first)
- Number of episodes of hypernatremia (serum sodium > 145 mmol/L) during ICU stay (or up to day 90, whichever occurs first)
- Glasgow coma scale at ICU and hospital discharge (see annex).
- Number of patients with an episode of stroke (medical diagnosis as registered in the medical file) during ICU stay (or up to day 90, whichever occurs first)
- Gastroduodenal bleeding requiring transfusion or hemostatic treatment during ICU stay (or up to day 90, whichever occurs first)

RECORDS" protocol, version 4.0 of 03/03/2021

34/61

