4.1.2 Interventional phase

4.1.2.1 ELIGIBILITY CRITERIA (INTERVENTIONAL PHASE)

4.1.2.1 Inclusion Criteria (interventional phase)

- 1) Patients \geq 18 years old;
- 2) Admitted to the ICU with proven or suspected infection as the main diagnosis;
 - 3) Community acquired pneumonia related sepsis OR vasopressors dependency (norepinephrine, epinephrine, vasopressin, dopamine, phenylephrine) OR septic shock (Singer 2016: vasopressor to maintain mean blood pressure of at least 65 mmHg and lactate levels above 2 mmol/l) OR acute respiratory distress syndrome (ARDS Ranieri 2012: a- acute onset, i.e. within one week of an apparent clinical insult and with progression of respiratory syndrome, b-bilateral opacities on chest imaging not explained by other pulmonary pathologies, e.g. pleural effusion, atelectasis, nodules etc, c- no evidence for heart failure or volume overload, d-PaO2/FiO2 ≤ 300 mm Hg, PEEP ≥ 5 cm H2O

4) Patient who has signed an informed and written consent whevener he/she is able of consent, if not, if not ascent from his/her representant whenever he/she is present at time of screening for inclusion

- 5) Patients who have been tested for one or more RECORDS specific biomarkers
 - o CIRCI
 - o Endocan
 - o GILZ <
 - o CPD
 - o Transcriptomic SRS2
 - o Endotype B
 - o PCR COVD-19
 - o PCR Influenza
 - o PCR other respiratory virus

6) Affiliation to a social security system or to an universal health coverage (Couverture Maladie Universelle, CMU);

7) Patients under guardianship or curatorship will be included;

8) Patients in case of simple emergency (legal definition) will be included.

RECORDS" protocol, version 4.0 of 03/03/2021

16/61

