4.1.2 Exclusion Criteria (interventional phase)

1) Pregnancy;

- 2) Expected death or withdrawal of life-sustaining treatments within 48 hours;
- 3) Previously enrolled in this study;
- 4) Formal indication for corticosteroids according to most recent international guidelines
- 5) Vaccination with live virus within past 6 months
- 6) Hypersensitivity to hydrocortisone or fludrocortisone or any of their excipients (SPC)
- 7) Women of childbearing potential not using contraception
- 8) Nursing women

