9.2 STATISTICAL METHODS

9.2.1 Adaptive Bayesian analyses

Clinical trial methodology needs to adapt to personalized medicine by including more frequent interim analyses of accumulating data, or by making greater use of those biomarkers information (Saad 2017; Janiaud 2019). An adaptive design is a clinical trial design that allows adaptations or modifications to aspects of the trial after its initiation without undermining the validity of the trial.

Therefore, the aim of the sequential analyses will be to detect treatment-by-biomarker interactions, that is, whether the treatment effect may be different according to biomarkers, that may potentially stop the recruitment of patients presenting with certain levels of that biomarker if there is any evidence that it interacts negatively with the outcome. Treatment effect will be assessed on two main outcome measures, namely a tolerance measure (to detect potential deleterious effects of treatment in some subsets) and an early surrogate efficacy measure (to detect a potential futility to continue treatment evaluation in some cohorts). As described above (section 4.8.2), the tolerance measure will be the occurrence within the first RECORDS" protocol, version 4.0 of 03/03/2021

7, 14 and 28 days of any grade 3 or over adverse events such as hospital-acquired infections, hyperglycemia, hypernatremia, neurological disorders, and the efficacy measure will be the number of vasopressor-free days within the first 28 days.

Search for treatment-by-cohort interactions will be based on each endpoint, and each cohort, separately. Let A and B denote the 2 treatment arms. The treatment effect, 0, of A over B will be considered as the parameter of interest.

Let consider a set of K biomarkers available at baseline, with $x_i = (x_{1i}, \dots, x_{Ki})$ the set of biomarkers for subject *i*, and $Y_{ii} = 1$ the outcome of subject i in arm j.

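### Vasopressor-free days, the interim efficacy measure, score 0 only for death on vasopressors, so a patient weaned early who then dies can outscore a survivor weaned late; organ-dysfunction-free days have no death rule of their own

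*Protocol*

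**What the plan says.** Section 9.1 states: "Sequential analyses will use the number of vasopressor-free days at day 28 as the measure of efficacy". Section 9.2.1 repeats that "the efficacy measure will be the number of vasopressor-free days within the first 28 days" and gives the measure its role: "an early surrogate efficacy measure (to detect a potential futility to continue treatment evaluation in some cohorts". It therefore bears on whether recruitment into a biomarker cohort continues.

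The scoring is in section 5.14.2.

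- **Item 2, vasopressor-free days:** "defined as the number of days with permanent hemodynamic stability in the absence of any vasopressor agent". The only provision for death is "When a patient will die on vasopressor therapy, the corresponding vasopressor free day will be 0".
- **Item 3, ventilation-free days:** the same pattern. The zero applies "When a patient will die on mechanical ventilation or will be discharge home on mechanical ventilation".
- **Item 4, organ-dysfunction-free days:** defined by a total SOFA of 6 or less. It then repeats the item 2 sentence about vasopressor-free days word for word.

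For the primary outcome, section 5.14.1 classes any death in the first 90 days as negative, whatever support the patient was on.

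**The concern.** A count of support-free days gives a usable ordering only if death cannot score better than survival. Here death scores 0 in one circumstance only. A patient who comes off vasopressors and then dies keeps the days already earned. On one reading of the text, the patient also keeps the days after death.

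Two consequences follow. The interim measure and the primary outcome can rank the same two patients in opposite order. A treatment that changes how patients die, or that speeds weaning while adding later deaths, can also look better at an interim than it is. Because the measure informs cohort futility, a cohort could be carried forward on an apparent benefit that the primary outcome would not share.

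Item 4 is a plain drafting error. Its death sentence concerns a different outcome, so organ-dysfunction-free days are undefined for patients who die.

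**Working it through.** **1. The plan's own figure.** Inputs from section 9.1: 176 per arm, difference 3 days, SD 10, alpha 0.05 (taken as two-sided). Standard error = 10 × √(2/176) = 1.066, and 3/1.066 = 2.814. Normal power = Φ(2.814 − 1.960) = 80.4%; the noncentral t gives 80.1%. The stated 80.04% is reproduced, so the 352-patient arithmetic is sound.

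**2. Ranking, which needs no assumed rates.**

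| Patient | Item 2, days alive | Item 2, days after death counted | 0 for any death |
|---|---|---|---|
| Weaned day 4, dies day 24 off vasopressors | 24 − 4 = 20 | 28 − 4 = 24 | 0 |
| Survivor, weaned day 10 | 28 − 10 = 18 | 18 | 18 |

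If the day of death is not counted, the first score is 19, still above 18.

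**3. Effect on the arm difference, under assumed rates.** None of these rates is in the protocol. Weaning times are exponential with mean m and independent of the patient's fate. Survivors then average M = 28 − m(1 − e^(−28/m)), so M = 22.06 for m = 6 and 23.02 for m = 5. Deaths on vasopressors score 0. Each death off vasopressors keeps an average credit C, which depends on when death follows weaning:

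- Uniform between weaning and day 28: C = M/2 = 11.03 (m = 6) or 11.51 (m = 5).
- Exponential gap with mean g, capped at day 28: C = g[(1 − e^(−28/m)) − e^(−28/g)(1 − e^(−28k))/(mk)], with k = 1/m − 1/g. For g = 7, C = 6.50 or 6.62. For g = 3, C = 2.94 or 2.97.
- Days after death counted: C = M.
- Zero for any death: C = 0.

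Arm mean = (share surviving) × M + (share dying off vasopressors) × C.

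*Scenario A.* Mortality is 35% and m = 6 in both arms. Deaths on/off vasopressors are 20%/15% in control and 12%/23% in treated. The survivor terms cancel, so the difference is 0.08 × C.

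*Scenario B.* Control is as in A. Treated has m = 5 and deaths 14%/26%, so mortality is 40%. The difference is (0.60 × 23.02 − 0.65 × 22.06) + (0.26 × C₅ − 0.15 × C₆) = −0.53 + (0.26 × C₅ − 0.15 × C₆), where C₅ and C₆ are the credits for m = 5 and m = 6.

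| Treatment of deaths off vasopressors | A (days) | B (days) |
|---|---|---|
| Days alive, death uniform to day 28 | +0.9 | +0.8 |
| Days alive, mean 7 days after weaning | +0.5 | +0.2 |
| Days alive, mean 3 days after weaning | +0.2 | −0.2 |
| Days after death counted | +1.8 | +2.2 |
| 0 for any death by day 28 | 0 | −0.5 |

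For scale, the prior-trial difference quoted in section 9.1 is 17.1 − 15.0 = 2.1 days.

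**4. Secondary note on the planning inputs.** The 3-day, SD 10 figures stand beside a prior trial whose title in the bibliography concerns septic shock. Section 4.1.2.1 also admits patients without vasopressors: "Community acquired pneumonia related sepsis OR vasopressors dependency" or ARDS. Suppose a share q is never on vasopressors and scores 28 in both arms, while the rest have mean 16 (near the midpoint of 17.1 and 15.0), SD 10 and a 3-day effect. Then the difference is 3(1 − q) and the variance is 100(1 − q) + q(1 − q)(28 − 16)².

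| q | Difference | SD | t-test power, 352 patients |
|---|---|---|---|
| 0 | 3.0 | 10.00 | 80% |
| 10% | 2.7 | 10.15 | 70% |
| 20% | 2.4 | 10.15 | 60% |
| 30% | 2.1 | 10.01 | 50% |
| 50% | 1.5 | 9.27 | 33% |

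The protocol does not give q.

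**The case against.** **The word permanent in item 2 may already exclude patients who later deteriorate.** It might be meant that way, but it is not defined. If it removed credit from everyone who dies, the explicit zero for death on vasopressors would be redundant.

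**The size rests on when off-vasopressor deaths occur.** This stands. Counting days alive, Scenario B changes sign between a mean gap of 7 days and one of 3, and with short gaps the rule as written already shows harm. Only the range can be reported. For the same reason, a reader might infer that withdrawal of life support, with vasopressors stopped just before death, inflates the score substantially. If only days alive count, it adds almost nothing.

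**The measure is not the efficacy verdict.** This also stands. Section 9.2.1 uses it for cohort futility beside a separate tolerance measure of grade 3 or higher events. Mortality at day 28 is a secondary outcome, deaths are extracted yearly, a DSMB sits, and the primary outcome counts every death by day 90. A reader might infer that a harmful treatment would be declared effective; the documents do not support that. The more direct risk is a cohort continued on a misleading signal. Ventilation-free and organ-dysfunction-free days have no stated interim role.

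**Patients never on vasopressors do carry some information.** Survivors in that group all score 28, but their deaths lower the score if only days alive count, and patients who start vasopressors later contribute. The power figures also come from a t-test, whereas section 9.2.1 decides on the posterior probability of a ratio of effects. They do not show that any given cohort would look futile.

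**Conclusion.** The point holds as a flaw in a stated scoring rule. Section 5.14.2 item 2 leaves death off vasopressors without a score, and following the text puts some patients who die above some who survive. That inversion needs no assumed rates.

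The effect on an arm difference does need them. With equal 35% mortality and equal weaning, an 8-point shift of deaths from on- to off-vasopressor gives a false benefit of about 0.2 to 0.9 day, or about 1.8 if days after death count, against 0 when any death scores 0. With faster weaning and 5 points more deaths, the rule gives −0.2 to +0.8 day, or about +2.2, against −0.5. The rates and timing are illustrative.

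Item 3 shares the pattern, and item 4 has no death rule. The dilution in step 4 is a separate, secondary matter that depends on an unstated share; a death rule does not cure it. A reader might conclude that vasopressor-free days must be replaced as the interim measure. The documents do not compel that: a different interim outcome is a design choice open to the sponsor.

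**What to change.** 1. In section 5.14.2 items 2, 3 and 4, score 0 for any death by day 28, whatever support the patient was on at death. This also settles whether days after death count.
2. In item 4, replace the repeated vasopressor sentence with a death rule for organ-dysfunction-free days.
3. Restate the section 9.1 planning mean and SD under this definition before the first interim analysis, and say what share of patients is expected never to be on vasopressors.

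**Cost.** Wording in three items and restated planning inputs. Vital status and daily ICU vasopressor and ventilation data are already collected (sections 5.4 and 5.15). SOFA is scheduled only on set days (section 2.2 and the table in 5.8), so item 4 needs the death rule only and no added assessments. Moving to another interim outcome would be a larger design change and is not required here.
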